For aims 1, 3 and 4 each participant will be asked to complete a singular study visit that will last approximately 30-60 minutes. During this study visit, post consent, the individual may be asked to do the following:

- Find and install the Pattern Health app (aim 1 and aim 4)
- Register to the LIFT2 study (aim 1 and aim 4)
- Complete baseline survey (aim 1 and aim 4)
- Randomize to 1 of 3 groups or screen fail purposely (aim 1 and aim 4)
- Audio-recording for interview using qualitative analyses (aim 3)
- Provide feedback on app content and usability (aim 1, 3, and 4)

For aim 2, each consented patient will be asked to complete up to four individual study visits.

- **Baseline:** this visit is to occur post-consent (same day, ideally) at the time of hospital admission just prior to discharge. However, this visit may occur at the time of hospital discharge within 7 days of returning to home. At this visit, the following will occur:
 - App Registration
 - Baseline Survey Completion
- **T1 (Day 0) (+30 days):** this visit is to occur at the time of hospital discharge to home, ideally within the first week (7 days) of returning to home; however, it can occur up to 1 month (30 days) from the time of hospital discharge to home. At this visit, the patient will complete the T1 survey via the app, which includes the PHQ-9, PTSS, PHQ-10, and MAAS surveys. Score dependent, the patient will be randomized to 1 of 8 intervention combinations. If the patient's psychological distress score is too low; he/she will receive an automated alert via the app describing they are not eligible and their study participation is complete.
- **T2 (Day 30) (+60 days):** this visit is to occur post 1 month randomization for those patients who remain eligible to participate in the study. PHQ-9, PTSS, PHQ-10, and MAAS surveys will be administered again. If the patient's survey scores indicate high levels of distress, as defined by a triggered SI alert or increased distress score from T1, a delegated study team member will contact the patient for safety precautions.
- **T3 (Day 90) (+30 days):** this visit is to occur post 3 months randomization for those patients who remain eligible to participate in the study. PHQ-9, PTSS, PHQ-10, and MAAS surveys will

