As the project centers around Aim 2 (RCT), we calculated power for the test of a main effect or factor interaction in a constrained longitudinal general linear model with unstructured covariance matrix via simulation. Based on LIFT pilot data, the baseline standard deviation of PHQ-9 was assumed to be 5.3 and the covariance between time points ranged from 3.9 to 11.5. We examined a range of sample sizes at T2, from 120 to 200 participants. 500 simulated datasets were simulated under the alternative model, with power calculated as the proportion of times the estimated coefficient was found to be statistically significant at $p < 0.05$. Results indicated that with 192 total patients at T2 (24 per experimental condition; 240 total at T1 [randomization] assuming 20% dropout by T2), we will have $>90\%$ power to detect a factor main effect or factor interaction effect of 2 units on the PHQ-9 scale.

By targeting 240 randomized participants, we will have ample power to detect factor main and interaction effects even with deviations from our assumptions (e.g., higher dropout rate, misspecified covariance matrix, etc.). For Aims 3 and 4, these samples should be adequate for theme saturation.

10. Subject Participation Duration

Participating subjects in aims 1, 3 and 4 will be asked to participate in a singular study visit lasting 30-60 minutes. Participating subjects in aim 2 will be asked to participate for up to a total of 3 months. Participating in the factorial trial (aim 2) will require 1 month of daily, active participation in which the patient is practicing mMT daily and completing weekly check-ins. At the end of the 1 month (post T1 completion), the patient will be asked to complete T2 survey. Once the patient has completed the T2 survey, he/she is finished with active study participation for an additional 2 months at which time they will be asked to complete T3 survey.

11. Study Duration

We estimate that from the time the factorial experiment trial opens to enrollment during Month 9 of Year 1, it will require approximately 41 months to complete data collection (approximately 36 months for cumulative enrollment with 4-5 months to complete all long-term follow up; this time does not include start up and analyses) and 4-6 months to perform all final data analyses for all Aims.

12. Risk-Benefit Assessment

Potential risks

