Given the nature of this study, it is anticipated that most enrolled patients will not complete their study visits within the assigned protocol window. Additionally, it is expected that visits and/or mMTpractices will be missed. As such, these will not be considered protocol deviations. Should other protocol deviations or unanticipated problems occur, they will be discussed with the PI, documented, and reported to the IRB, study sponsor, and/or DSMB, as appropriate and when applicable.

Period and Frequency for Event Assessment and Follow-Up

Protocol deviations and other unanticipated problems, as well as AEs and SAEs, will be recorded in the data collection system throughout the study and reported, as appropriate, to the IRB, study sponsor, and/or DSMB, when applicable.

The study team will record all reportable events with start dates occurring any time after informed consent is obtained until 7 (for non-serious AEs) or 30 days (for SAEs) after the last day of study participation. At each study visit, the study team will inquire by way of verbal or written request and/or EMR review, of the occurrence of AE/SAEs since the last visit. Events will be followed for outcome information until resolution or stabilization.

Characteristics of an Adverse or Serious Adverse Event

Relationship to Study Intervention

To assess relationship of an event to study intervention, the following guidelines are used:

1. Related (Possible, Probable, Definite)
 - a. The event is known to occur with the study intervention.
 - b. There is a temporal relationship between the intervention and event onset.
 - c. The event abates when the intervention is discontinued.
 - d. The event reappears upon a re-challenge with the intervention.
2. Not Related (Unlikely, Not Related)
 - a. There is no temporal relationship between the intervention and event onset.
 - b. An alternate etiology has been established.

Expectedness

The Study PI will be responsible for determining whether an event is expected or unexpected. An event will be considered unexpected if the nature, severity, or frequency of the event is not consistent with the risk information previously described for the intervention.

Severity

The following scale will be used to grade adverse events:

1. Mild: no intervention required; no impact on activities of daily living (ADL)
2. Moderate: minimal, local, or non-invasive intervention indicated; moderate impact on ADL

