## 2.6 Data Decisions

Per the protocol, all participants with measures out of window will be removed from the analysis. The windows are as follows:

Time Point	Window
1 month post-randomization (T2)	Up to 60 days post-randomization (+30 days from 1 month)
3 months post-randomization (T2)	Up to 120 days post-randomization (+120 days from 3 months)

Records outside of that window are identified in the final dataset using an indicator called “outofwindow”.

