Given the factorial design, we will use effect coding, rather than dummy coding, for analyzing the effects of the intervention components. If the sample size is equal per condition, all of the tests of main effects and interactions are uncorrelated—that is, the main effect of a condition is the same even if other treatment conditions and interactions are included in the statistical model. Even with unequal sample sizes across conditions (as may occur with differential dropout by condition), if the imbalance is minor, the correlations between effects should be small.

Missing outcome data due to dropout or missing intermediate visits is expected to be at most 20%. Because the model will be fit using a full maximum likelihood method, we will be able to account for predictors of missingness in the model in order to obtain valid estimates of the main component effects, thanks to the property that the response can be missing at random (MAR) as defined by Little and Rubin. In practice, we will compare baseline characteristics of completers and non-completers. If we find that any covariates predict missingness, we will adjust for these variables in the model as a sensitivity analysis.

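### The SAP removes out-of-window measures that the protocol expects to be common, but neither the 20% missing-data allowance nor the N of 192 behind Table 2 makes room for them

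*Protocol*

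**What the plan says.** **Expected lateness.** In the protocol's section 12, under adverse events and unanticipated problems, "it is anticipated that most enrolled patients will not complete their study visits within the assigned protocol window". Missed visits and practices are expected as well, and the section concludes: "As such, these will not be considered protocol deviations".

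**Handling of late data.** SAP 2.6 states: "Per the protocol, all participants with measures out of window will be removed from the analysis". It then says that records outside the window carry an indicator in the final dataset, so it is unclear whether participants or records are meant. The supplied protocol defines visit windows in section 7 but states no removal rule. Its nearest statement, under post-randomisation failure in section 7, points the other way: a terminated participant is analysed up to the point of exclusion.

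**Windows.** The protocol gives "T2 (Day 30) (+60 days): this visit is to occur post 1 month randomization". SAP 2.6 gives "Up to 60 days post-randomization (+30 days from 1 month") for the same visit. The SAP's three-month row is labelled T2 and reads "Up to 120 days post-randomization (+120 days from 3 months"), which is inconsistent within itself.

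**Missing-data allowance.** SAP section 4: "Missing outcome data due to dropout or missing intermediate visits is expected to be at most 20" percent. Protocol section 9 bases its power on the same allowance, "with 192 total patients at T2 (24 per experimental condition; 240 total at T1 [randomization] assuming 20% dropout by T2"). SAP Table 2 and Appendix B use those 192 with complete data.

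**Analysis label.** Protocol section 9 and SAP section 4 both call the analysis intention-to-treat.

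**The concern.** One document expects lateness to be widespread, the other discards late data, and no calculation allows for the loss. A survey completed late is neither dropout nor a missed visit, so it lies outside the 20% as the SAP words it.

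Two things are at stake. The first is precision on PHQ-9 at T2, which drives the choice of components. The second is bias: the rule drops observed post-randomisation scores because of when they were given. Two of the three factors compare therapist contact with app delivery, so promptness could differ by factor level, and the exclusions would then differ by level too. Because lateness is not a deviation, deviation reports will not reveal it.

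**Working it through.** **Inputs.** From SAP Table 1 and Appendix B: Var(T1) = 27.95, Var(T2) = 19.28, Var(T3) = 11.78, Cov(T1,T2) = 9.67, Cov(T1,T3) = 3.91, Cov(T2,T3) = 11.54. N = 240 randomised and 192 at T2. Benchmark 1.6 points. Alpha 0.05, taken as two-sided.

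**Step 1: reproduce the plan's figure.** With baseline constrained equal, the relevant variance is that of T2 given T1:

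19.28 − 9.67²/27.95 = 15.93, so SD = 3.99.

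SE of a main effect = 2 × 3.99/√N. At N = 192 this is 0.576.

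Power = Φ(1.6/0.576 − 1.96) = 79.3%, against 79.8% in Table 2. The protocol's 2-point case gives 93.5%, in line with its claim of more than 90%. The plan's figures reproduce.

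**Step 2: check whether the allowance has slack.** 240 × 0.80 = 192. Dropout alone uses all of it.

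**Step 3: removal of participants (the literal wording).** Let q be the share of the 192 removed for lateness. Then N = 192(1 − q), in the same power formula. The documents do not give q, so a range is shown.

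**Step 4: removal of T2 records only, with every T3 kept.** The model then recovers part of the loss through T3. Given T1:

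- Var(T3) = 11.78 − 3.91²/27.95 = 11.23
- Cov(T2,T3) = 11.54 − 9.67 × 3.91/27.95 = 10.19
- squared correlation r² = 10.19²/(15.93 × 11.23) = 0.58

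With n = 192(1 − q) observed at T2 and 192 at T3:

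SE = 2 × √{15.93 × [(1 − r²)/n + r²/192]}.

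At q = 50%: 2 × √{15.93 × [0.42/96 + 0.58/192]} = 0.687, and Φ(1.6/0.687 − 1.96) = 64%.

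| q | T2 scores left | T2 missing, of 240 | Power, participants removed | Power, T2 records removed |
|---|---|---|---|---|
| 0 | 192 | 20% | 79% | 79% |
| 10% | 173 | 28% | 75% | 77% |
| 20% | 154 | 36% | 70% | 75% |
| 30% | 134 | 44% | 64% | 72% |
| 50% | 96 | 60% | 50% | 64% |

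The last column is favourable, because it assumes that no T3 score is lost. Under the literal wording, a late T3 alone could also remove a participant whose T2 was on time.

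**The case against.** The strongest reply is that the protocol sentence explains why late visits go unreported as deviations; it does not forecast missing T2 data. It speaks of enrolled patients and study visits, names no visit and gives no rate. Lateness at baseline or T1, or only at T3, could put a patient among the majority, whereas the SAP rule covers only T2 and T3. This stands. A reader might infer that more than half of the T2 scores will be lost and that the stated power cannot be reached. The documents do not support that.

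Lateness and dropout may also overlap. Protocol section 7 declares loss to follow-up after at least three contacts spaced 1 to 5 days apart, with one further week to respond. If contact starts near day 30, this can end by day 30 + 2 × 5 + 7 = 47, before the SAP's day 60. Some very late patients may therefore already be counted in the 20%. This stands too. The overlap cannot be sized, because the start of contact is not fixed.

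The window mismatch matters here. Read like the other visits, the protocol's T2 window runs to day 30 + 60 = 90. If both documents used that limit, few T2 scores obtained before the T3 survey would be lost. If both used day 60, the conflict would remain in full. So this point and the mismatch have to be settled together.

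A bounded window is a legitimate way to protect a one-month outcome, and the flag already makes an all-data analysis feasible. But the plan specifies no such analysis, and the primary result would still rest on the reduced set.

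SAP 2.3 says that 240 gives ample power even with higher dropout. At the nearly 40% loss of the earlier trial it cites, N = 240 × 0.60 = 144, SE = 2 × 3.99/√144 = 0.665, and power for 1.6 points is 67%. The statement does not close the gap.

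**Conclusion.** The conflict between the documents is real and affects the primary analysis. The missing-data allowance has no room for window exclusions, so the stated 80% power for 1.6 points fails to the extent that the protocol's expectation applies to T2 and the late patients are not already counted as dropout. Over an assumed range of 10 to 50% of the 192, power is 75 to 50% if participants are removed and 77 to 64% if only T2 records are. The calculation takes the SAP's covariance matrix as correct and assumes that exclusions fall evenly across the conditions.

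Removing observed scores because of their timing is also inconsistent with an intention-to-treat label. A reader might go further and infer that the factor effects will be biased because late responders are sicker or less prompted at the app levels. That is possible, but nothing in the documents shows it. The protocol describes reminders for participants generally (section 4) and frequent telephone contact with most of them (section 12).

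**What to change.** 1. Reconcile the T2 window between protocol section 7 (day 30, +60 days) and SAP 2.6 (up to day 60), and correct the label and the +120-day gloss in the SAP's three-month row.
2. In SAP 2.6, delete the attribution to the protocol and the removal rule. Keep in the primary model every observed T2 PHQ-9 completed before the T3 survey opens, and keep late T3 scores.
3. Specify the in-window-only analysis as a sensitivity analysis, and report the proportion late at T2 and T3 by factor level.
4. If the sponsor keeps removal, state whether records or participants are removed, and restate the expected missingness in SAP section 4 and the N and power in Table 2 to include window exclusions.

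The cost is SAP wording and one additional model run. The drawback is more spread in assessment timing around the one-month estimate; the in-window sensitivity analysis shows whether that matters. The change should be made before the outcome data are analysed, since the rule determines which scores drive component selection.

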- **Post Randomization Failure:** defined as any patient who consents to the study, completes the initial study visit, is discharged to an independent home setting, completes survey T1 and is randomized to the study, and anytime during the first month study participation is re-admitted to the hospital. Should this occur, the patient may be terminated if the hospitalization lasts ≥ 7 days and/or the patient is unwilling or unable to continue study procedures.
 - *Note: If the participant is terminated, he/she will be included in the analyses up to the point that they were excluded.*
- **Withdraw by PI or Self:** defined as any individual who voluntarily consents to participate in the study, but is then withdrawn from the study.
 - The PI may withdraw a participant at any time without their consent if the PI deems it is in their best interest to no longer participate OR the patient demonstrates continuous lack of compliance with study protocol and study procedures.
 - The patient may withdraw themselves at any time; the study team will be asked to document the reason for withdraw for study records.

Patients who reach this status will have no additional follow-ups or study requirements. Patients who are assigned this status must be maintained on the enrollment log. A reason for withdraw should be recorded in the study records.

- **Lost to Follow-Up (LTF):** defined as any individual who voluntarily consents to participate in the study but after non-compliance and at least 3 documented, attempted contacts appropriately spaced 1-5 days apart, the individual will be considered LTF.
 - For aim 2 only:
 - Patients who reach this status will have no additional follow-ups or study requirements. Patients who are assigned this status must be maintained on the enrollment log.
 - A patient who returns the study team's contacts within 1 week of last attempted contact may resume study participation.
- **Completed:** defined as any individual who both consented and randomized to the study and completed T1-T3 (aim 2 only) or any individual who completed assigned study visit (aims 1, 3 and 4). Individuals who reach this status have no additional follow-up or study requirements. Individuals who are assigned this status must be maintained on the enrollment log.

Study Visits

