 - The study personnel will notify the site PI one of the other PIs immediately
 - The study personnel will stay on the telephone with the subject participant.
 - The study personnel will immediately contact 911 to initiate an on-site rescue if such action is clinically indicated.
 - The study personnel will stay on the telephone with the subject until EMS services have contacted the participant.

If the participant is determined to be actively suicidal and require immediate medical therapy, they will be withdrawn from the study.

As described above, all concerns about participant safety will be discussed immediately with the PI - including concerning severe distress that does not involve suicidality.

For these situations, once an “alert situation” is known, the PI will refer the participant if needed (based on a PI-led phone call) to local psychological resources. The study team will also make urgent and emergency referrals as needed based on information learned.

To date based on some studies that have included over 400 participants, we have found that <5% of participants will require a call from the PI during some point in the study period. Of those, none has required referral to acute psychiatric care after a detailed interview from the PI. After a disposition / solution has been made, both the resolution (and follow up) will be documented in the ‘contact log’ section of the data system for reporting to the DSMB.

Patient Death While in Study

Finally, we recognize that we are working with a critically ill population that is at risk for death during follow up due to their underlying illness. Before T2 and T3 data collection, the study team will review the EMR to look for records of death, halting all study procedures if death has occurred and noting the date. On phoning any participant, the study team will initiate a conversation to tactfully ascertain the patient's vital status should a family member answer first. If the patient has died, the study team will provide brief support and their condolences.

Withdraw While in Study

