Appendix 1: Schedule of Events

	Day 0 (In-Hospital, Baseline)	Day 1 , T1 (Discharge) (+30 days)	Week 1	Week 2	Week 3	Week 4 Day 30, T2 (+60 days)	Day 90 (+30 days), T3
Screening*	X						
Consent (a)*	X						
App Registration*	X						
Baseline Survey (b)*	X						
Usability Survey*							
T1 Survey (c)		X					
T2 Survey (c)						X	
T3 Survey (c)							X
Weekly Check-In (d)			X	X	X		
Data Entry (e)	X	X				X	X
AE/SAE assessment (f)	X	X				X	X
Survival Status (f)		X				X	X
End of Study (g)							X

- a) Patients may be approached and consented during their admission, if well enough; their hospitalization (e.g., while in step-down), or within 7 days of returning to their home for participation in the study.
- b) Completion of the baseline survey includes the patient providing self-reported information such as social and demographic information and general health status.
- c) Surveys 1, 2 and 3 will be completed via the app by all study participants, regardless of intervention combination assignments.
- d) For those participants randomized to 1 of the 8 intervention combinations, they will complete a weekly check-in to ascertain overall safety of the patient and usefulness of coping skills practice.
- e) AE/SAE assessment and survival status will be completed via EMR review and/or telephone interview.
- f) Study completion for patients enrolled in the study is considered to occur at the completion of T3. However, participants may undergo EOS if they are withdrawn from the study by the PI or opt to withdraw from the study voluntarily at any time. Should withdraw of a patient occur, the reason for withdraw and date of withdraw will be documented. AE/SAEs and survival status will be noted, as applicable.

*For aim 1 only.

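### The protocol commits to recording AEs for 7 days and SAEs for 30 days after participation ends, but plans no active ascertainment in that window

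*Protocol*

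**What the plan says.** **Recording period.** Protocol section 12 (Period and Frequency for Event Assessment and Follow-Up) has the team record all reportable events that start after consent, "until 7 (for non-serious AEs) or 30 days (for SAEs) after the last day of study participation".

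**How events are found.** The same paragraph continues: "At each study visit, the study team will inquire by way of verbal or written request and/or EMR review, of the occurrence of AE/SAEs", looking back to the previous visit. Appendix 1 gives the method: "AE/SAE assessment and survival status will be completed via EMR review and/or telephone interview". (This text stands at footnote e, although the table rows carry the letter f.)

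**When participation ends.** Appendix 1 states: "Study completion for patients enrolled in the study is considered to occur at the completion of T3". Section 7 (Study Visits) also ends participation at T3, provided that high distress does not call for further contact.

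**What happens afterwards.** For withdrawn participants, and again for those lost to follow-up in Aim 2, section 7 says: "Patients who reach this status will have no additional follow-ups or study requirements". The definition of completed status says the same in nearly the same words. For withdrawals, Appendix 1 adds that AE/SAEs and survival status are noted where applicable, without giving a date or a later contact.

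**Deaths.** Section 12 (Patient Death While in Study) says: "Before T2 and T3 data collection, the study team will review the EMR to look for records of death". No later check is described.

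The SAP does not deal with safety follow-up.

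**The concern.** A recording period is only as good as the procedure that fills it. Here the period extends beyond the last visit, while the procedure is attached to visits. A site that followed the schedule and the status definitions exactly would have no planned step for finding an event in the window that section 12 sets.

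The events concerned are plausible in this population. Section 12 defines an SAE as a suicide attempt, a hospitalization after the index stay, or death. It describes the participants as at risk of death during follow-up, and section 14 promises close scrutiny of deaths in that period. If the post-participation window is never actively examined, a low count there cannot be told apart from a low level of looking. What is at stake is the completeness of the safety data, not the efficacy result.

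**Working it through.** The plan gives no figure to reproduce. The check is a day count of the recording period against the scheduled assessments, with randomization at T1 as day 0.

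**Inputs**

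| Item | Value | Source |
|---|---|---|
| AE period after last day | 7 days | Protocol section 12 |
| SAE period after last day | 30 days | Protocol section 12 |
| AE/SAE assessments | Baseline, T1, T2, T3 | Protocol Appendix 1 |
| Survival checks | T1, T2, T3 | Protocol Appendix 1 |
| T3 timing, *t* | Day 90 to day 120 | Protocol section 7; the upper limit also in SAP section 2.6 |
| Time allowed for follow-up | 4-5 months | Protocol section 11 |

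**Completers.** The last scheduled inquiry covers events up to day *t*.

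- End of AE period: *t* + 7, which is day 97 if *t* = 90 and day 127 if *t* = 120.
- End of SAE period: *t* + 30, which is day 120 or day 150.
- Share of the post-randomization SAE period with no scheduled assessment: 30/(*t* + 30). This is 30/120 = 25% if *t* = 90 and 30/150 = 20% if *t* = 120.

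The recording period starts at consent, before randomization, so the share of the whole period is somewhat lower. A T3 completed later than day 120 also lowers the share. The 30 days themselves do not change.

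**Early leavers.** For withdrawal on day *w*, days *w* to *w* + 30 have no scheduled assessment, a share of 30/(*w* + 30). As an illustration, *w* = 15 gives 30/45 = 67%. The day is assumed, since the documents give no distribution of withdrawal times. Participants terminated after a readmission are in the same position: section 7 says only that their data are used up to that point, and no later check is scheduled.

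**Room in the timetable.** The latest in-window T3 plus 30 days is 120 + 30 = 150 days, about five months. That fits the upper end of the 4-5 months allowed, but no procedure is assigned to the last 30 days.

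**What cannot be computed.** The documents give no rate of hospitalization or death after T3 or after withdrawal, so the number of events that would be missed cannot be stated.

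**The case against.** The best defence is that the duty to record also covers events learned of passively, and that several such routes exist. Participants can reach the PI at any hour, section 12 speaks of frequent telephone contact with most participants, and high distress at T3 leads to further contact. Known events are followed until they resolve or stabilize, so a participant who leaves because of suicidality or a long readmission has a stated route for that event. The sentence on no further follow-up can be read as describing what is asked of the patient, which would leave staff free to review the record. The DSMB charter is to set out adverse event reporting, and neither it nor the consent form is among the documents reviewed. Finally, active training lasts four weeks, so a completer's window opens about two months after the intervention ends.

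Much of this stands. It rules out four stronger readings that a reader might infer:

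- **That nothing would be collected in the window.** The passive routes could bring events to light. What is missing is a planned, systematic step, including one for a new event in someone who has already left.
- **That 20% of 240, or 48 participants, would never be checked after leaving.** The 20% in protocol section 9 is dropout by T2, and SAP section 4 counts missed intermediate visits in its 20%. Someone who misses a survey without being withdrawn or declared lost still falls under the record check for deaths before T3.
- **That those who leave do so largely because of suicidality.** The documents do not say so. Section 12 reports that, in studies of over 400 participants, fewer than 5% needed a call from the PI and none needed acute psychiatric referral.
- **That the DSMB's comparison between factor groups would be biased.** Among completers the gap has the same length in every group. Bias would need departures to differ by factor level, which is not shown. The tests are made only on request, and the DSMB reviews dropout at each meeting.

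The defence does not remove the inconsistency. Passive routes depend on chance, a permissive reading of section 7 is not an instruction to look, and the protocol should be workable without a charter that may or may not fill the gap.

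**Conclusion.** The point holds in this form: the protocol sets a recording period of 7 days (AEs) and 30 days (SAEs) after participation and plans no active ascertainment in it. For SAEs and deaths the unassessed stretch is 20% to 25% of a completer's post-randomization period, depending on whether T3 falls on day 120 or day 90, and the full 30 days after any withdrawal. The range rests on T3 being done within its stated window and on counting from randomization.

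The consequence is incomplete safety data of unknown extent. Nothing here affects the PHQ-9 analysis, and neither document announces a tabulation that would misstate the period covered. The change should be made because sections 7 and 12 and Appendix 1 do not agree and the correction is cheap. It is not a threat to the trial's main conclusion.

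**What to change.** Reconcile sections 7 and 12 with Appendix 1 in one of two ways.

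1. **Fill the window.** Add to Appendix 1 one SAE and survival check by EMR review, 30 days after T3, withdrawal, termination or loss to follow-up, where permission for record review remains. State the date from which the 30 days run for each type of exit. Say in section 7 that the absence of further follow-up does not exclude this safety review.
2. **Shorten the commitment.** End the recording period at the last scheduled assessment.

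If the 7-day AE period is kept, state that it rests on spontaneous report: AEs here are mainly suicidal ideation and questionnaire-related distress, which a chart will often not show. Under either option, report events by the window actually assessed.

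The first option costs protocol wording and one chart review per participant by existing staff, with no participant contact, using a method that section 12 and Appendix 1 already allow. Its limit is that the review may miss admissions and deaths outside the site's own records, and the report should say so. The second option costs wording only, but gives up any claim to safety data after T3 or after withdrawal.
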